7. STATISTICAL CONSIDERATIONS

The statistical analysis plan for this study will be described in detail in a separate Statistical Analysis Plan (SAP). The initial phase of this study is defined as *Part A* and represents the randomized double-blind portion of the study. Part B is the open-label extension phase where all subjects will receive active therapy.

The primary population for assessing efficacy and safety will be the *Intent to Treat (ITT) Analysis Set*, defined as all subjects who were enrolled into the study and issued a study device.

A secondary analysis of the individual efficacy endpoints will be conducted using the *Per Protocol* (*PP*) *Analysis Set*, defined as all subjects who were enrolled and completed \geq 70% use in treating with the study device.

Subjects will complete a 14-day run in period to obtain an average over the last 7 days in the runin period to obtain the NPRS score for qualification. Once the subject is determined to be eligible, the subject will be enrolled and randomized 1:1 to either an active or inactive sham device and become part of the *ITT and PP sets*.

Subjects in the *ITT and PP sets* will be instructed in the use of the devices for 120 days in the home environment. At months 1, 2, and 3 subjects will return to the clinic to complete PGI and review of adherence to treatment and diary entries. At month 3, subjects will return for completion of the WPAIQ, NeuroQoL and SPP measurements. Subjects will return to the clinic at day 121 for final evaluation and to complete the questionnaires, SPP, QST, and NCS.

7.1 Summarization of Results

The tabulations will be based on the results for the change from baseline to study day 120. Supportive subject data listings will be sorted and presented by subject number, visit date and relative study day. Listings will also include the number of days relative to the initiation of treatment. Summary tabulations will be created for all randomized subjects who complete the baseline and study day 120 evaluations (*Completers Analysis Set*), and all randomized subjects using the baseline and last recorded set of evaluations (*End of Study Evaluation Set*). This latter set should include all subjects who were randomized and complete at least one set of evaluations after randomization.

Specific algorithms will be described in the Statistical Analysis Plan for imputing missing or partially missing dates, if deemed appropriate, under specific data topics. Imputed or derived data will be flagged in the individual subject data listings. Imputed data will not be incorporated into any raw or primary datasets. The imputed data will be retained in the derived / analysis datasets.

The total duration for a subject *on-study* will be calculated as the difference between the date of initial study treatment and the last day of observation plus 1 day. All calculations for defining the duration on-study will follow the algorithm DURATION = [STUDY COMPLETION OR WITHDRAW DATE – INITIAL TREATMENT DATE + 1].

Summary statistics will consist of the count and percentage in each level for categorical variables, and the sample size (n) mean, median, standard deviation (SD), minimum, and maximum values for continuous variables. Pairwise differences between the treatment groups will be calculated and 95% confidence intervals constructed. Time to event analysis will be determined through Kaplan Meier analysis and log-rank testing.

All summary tables will include the analysis population sample size (i.e., number of subjects). Study Day 1 is defined as the day the subject receives their initial exposure to the study device. All *study days* are determined relative to the day of initial treatment with the study device. Baseline values will be defined as those values recorded closest to, but prior to, the first active study treatment.

The primary endpoint for the study is the change from baseline in the NPRS score at 4 months.

The primary hypothesis to be tested is presented below:

Ho: μ (Change in NPRS score at 4 months / PEMF group) = μ (Change in NPRS score at 4 months / sham group)

Ha: μ (Change in NPRS score at 4 months / PEMF group) $\neq \mu$ (Change in NPRS score at 4 months / sham group)

To compare the absolute change in pain from baseline to 4-months, the intra-patient change will be calculated and serve as the dependent variable in the analysis. The baseline pain score will be introduced in the model as a covariate. Clinical site will be added to the model to assess poolability of the data across sites. Interaction between clinical site and treatment will be evaluated using a type 1 error rate of 10%.

Mixed Models with Repeated Measures (MMRM) comparing results across all time-points will also be performed, adjusted for the baseline value, week, treatment by week interaction and the effect of the patient.

Sub-group analysis will be pre-specified in the SAP and will be performed on subjects with pain scores ≥ 5 as well as subjects with A1C above and below 8.5.

Missing or Incomplete Data

If a patient reports at least 3 days with non-missing pain intensity scores within a particular week, the weekly mean pain intensity score will be derived using the non-missing scores only. This is identical to imputing the missing scores as the mean of the non-missing scores. If the patient reports less than 3 days with non-missing pain intensity scores within a particular week, the weekly mean pain intensity score will be treated as missing data.

Missing weekly mean pain intensity scores will be imputed using multiple missing data and pattern mixture methodology. Sensitivity analyses will be conducted exploring different patterns for missing data. An MMRM will be performed using only observed data without multiple imputation

and an analysis using the change from baseline to the last non-missing weekly mean pain intensity score will also be provided.

The pattern mixture model methodology will be implemented using SAS procedures MI and MIANALYZE. Specifically, the following steps will be followed:

• Intermittent missing data will first be imputed using the Markov Chain Monte Carlo (MCMC) method implemented with the SAS MI procedure, which is appropriate for non-monotonic missing data.

Data for patients who discontinues early will be multiply imputed as follows:

- If the patient discontinues due to an AE lack of response, then missing data will be assumed to follow a distribution similar to the baseline values observed in the patient's randomized treatment.
- If the patient discontinues due to reasons other than AE or treatment response, at each time point, missing data will be assumed to follow a distribution similar to scores for patients that are still in the study and randomized to the same treatment group.

Results of the 120-day results, and the MMRM using the multiply imputed data, will be summarized using the SAS MIANALYZE procedure.

A hierarchical approach will be undertaken for the pre-specified secondary outcomes. Testing will occur in the listed sequence following testing of the primary endpoint.

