3.4 Eligibility Criteria

Eligibility for participation in this study will be based on the inclusion/exclusion criteria. An individual subject may only be included in the study once.

Inclusion Criteria

- 1. Subject has documented Type 1 or Type 2 diabetes mellitus according to the ADA criteria (Appendix B).³³
- 2. Subject has daily pain attributed to symmetrical lower extremity diabetic peripheral neuropathy for at least 6 months prior to screening. Confirmed by score of ≥ 6 on the Toronto Clinical Neuropathy Scoring System.
- 3. Subjects' average lower extremity pain related to diabetic peripheral neuropathy over the preceding 24 hours is ≥4 and <9 based on the 11-point NPRS (0-10) at the Screening Visit.
- 4. Subject age is greater than or equal to 22 years and less than 80 years of age.
- 5. Subject is on stable diabetes treatment which should include medication and/or diet and exercise for at least 3 months prior to Screening.
- 6. Subject has an HbA1c $\leq 10\%$ at Screening or within 3 months of Screening.
- 7. Subject has not changed their analgesic prescriptions in the preceding one month.
- 8. Subject has an ankle-brachial index (ABI) of ≥ 0.8 to ≤ 1.3 . If the subject has incompressible vessels, a toe brachial index of 0.8 to 1.3 is required. These adequate lower extremity studies are with no documented intermittent claudication.
- 9. Subject walks independently with or without assistive devices, and does not require a wheel chair.
- 10. Subject is willing and able to give written informed consent and to comply with all parts of the study protocol.

- 11. Female subjects must be post-menopausal, surgically sterile, abstinent, or, if of childbearing potential, practicing (or agreeing to practice) an effective method of birth control if they are sexually active for the duration of the study. Effective methods of birth control include prescription hormonal contraceptives, intrauterine devices, doublebarrier methods, and/or male partner sterilization.
- 12. Subject can access an internet browser in the home environment or through a smart phone.

Enrollment Visit Inclusion Criteria

- 1. Average diabetic peripheral neuropathic pain intensity (NPRS score) is ≥ 4 and < 9 calculated as the mean of the daily NPRS scores for neuropathic pain in the lower extremities over the 7 days preceding the visit.
- 2. Subject has completed a minimum of 70% of the ePRO assessments during the run-in period.

Exclusion Criteria

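### Protocol 7.1 imputes adverse-event and lack-of-response dropouts from the arm's baseline distribution, with no tie to the patient's own baseline, which adds avoidable noise to a change-from-baseline analysis

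*Protocol*

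**What the plan says.** Protocol 7.1 (Missing or Incomplete Data) sets out a stepwise multiple imputation of missing weekly mean pain scores. "Intermittent missing data will first be imputed using the Markov Chain Monte Carlo (MCMC) method"; early discontinuations are then handled by reason.

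- Adverse event or lack of response: "missing data will be assumed to follow a distribution similar to the baseline values observed in the" arm to which the patient was randomised.
- Any other reason: at each time point the missing score is taken as "similar to scores for patients that are still in the study and randomized to the same treatment group".

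Neither sentence mentions the patient's own baseline or earlier weeks, and the model to be run in PROC MI is not specified. For the primary analysis, "the intra-patient change will be calculated and serve as the dependent variable in the analysis", and "The baseline pain score will be introduced in the model as a covariate".

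Protocol 7.1 also plans sensitivity analyses on missing-data patterns, an MMRM on observed data and an analysis of the last non-missing weekly mean. SAP 7.2 differs: missing values are not imputed (only dates have a method), and the ITT comparison uses the last recorded observation.

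**The concern.** The rule replaces a patient's missing score with one typical of the arm at baseline. The analysis then subtracts that patient's own baseline. The result mixes the spread between patients into a quantity meant to measure change within a patient. Section 3.4 admits a wide range ("Average diabetic peripheral neuropathic pain intensity (NPRS score) is ≥ 4 and < 9"), so the imputed change for one person can exceed the 1.07-point difference that the trial is powered to detect, in either direction.

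At stake are the precision of the primary comparison and, if imputed scores are used there, the 2-point-or-30% responder classification.

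**Working it through.** **Inputs from the documents.** Difference 1.07, SD 1.83, 62 per group before inflation, 85 per arm enrolled, 30% discontinuation (Protocol 7.4). Baseline from 4 to below 9 (Protocol 3.4). Response is a fall of 2 points or 30% (SAP 3.1.1).

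**Assumptions, since the documents give no figure.** Baselines are normal, truncated to 4–9, with various means and SDs. One third to two thirds of dropouts leave for an adverse event or lack of response. The within-patient week-to-week SD is 0.3 to 0.7.

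**1. The plan's own figure.** n = 2 × (1.960 + 1.282)² × (1.83/1.07)² = 61.5, so 62 per group. This reproduces. The protocol gives no figure for the imputation rule itself.

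**2. One patient.** Under a literal draw, expected imputed change = arm baseline mean − own baseline.

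| Assumed arm mean (SD) | Enters at 8.5 | Chance of response at 8.5 | Enters at 4.0 |
|---|---|---|---|
| 5.64 (0.88) | −2.86 | 83% | +1.64 |
| 6.10 (1.05) | −2.40 | 65% | +2.10 |
| 6.50 (1.07) | −2.00 | 50% | +2.50 |
| 6.87 (1.10) | −1.63 | 37% | +2.87 |

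Check of row 2: a patient at 8.5 responds if the draw is 6.5 or less; (6.5 − 6.10)/1.05 = 0.38, which is 65%. In every row a patient entering at 4.0 is never imputed as a responder.

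**3. All such failures.** If their baselines match the arm's, the mean imputed change is 0.00. If the log-odds of dropout rise by 0.5 to 1.0 per baseline point, it is about −0.4 to −0.8.

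**4. Treatment estimate.** ANCOVA simulation: 85 per arm, 1,500 runs per scenario, one draw per missing value, true difference −1.07.

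| Failures active/sham | Log-odds of dropout per baseline point | Estimate, arm draw | Estimate, own baseline | Power, arm / own |
|---|---|---|---|---|
| 15% / 15% | 0 | −0.911 | −0.911 | 0.901 / 0.916 |
| 15% / 15% | 1.0 | −0.843 | −0.849 | 0.871 / 0.880 |
| 10% / 25% | 1.0 | −0.950 | −1.014 | 0.935 / 0.963 |
| 25% / 10% | 1.0 | −0.706 | −0.629 | 0.726 / 0.629 |

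Row 1 is 0.85 × 1.07 = 0.91, as expected under either rule. The largest gap is 0.706 − 0.629 = 0.077. In the last row the arm draw has the higher power, because its estimate is larger.

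With no true effect and equal failure rates, the arm draw rejects in 4.7 to 5.7% of runs. With unequal failure rates both rules reject more often (11 to 16% arm draw, 15 to 18% own baseline). With dropout unrelated to baseline the two nearly agree (15.9% and 16.6% for 10%/25%), so the excess comes from treating failures as unimproved on average, which both rules do.

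**5. Noise.** By hand, take a failure's residual variance as 1.05² = 1.10 for the arm draw and 0.5² = 0.25 around own baseline, and 1.83² = 3.35 for other patients. With failures at 10% of the arm: √[(0.9 × 3.35 + 0.110)/(0.9 × 3.35 + 0.025)] = 1.014. At 20%: √[(0.8 × 3.35 + 0.220)/(0.8 × 3.35 + 0.050)] = 1.031.

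Full multiple-imputation simulation (1,500 trials, 20 imputations, Rubin's rules, 30% dropout) for failure shares of one third, one half and two thirds of dropouts:
- SE 0.320 against 0.313, 0.312 against 0.302, and 0.304 against 0.288: 2.2%, 3.3% and 5.6% larger.
- Power 0.856 against 0.869, 0.825 against 0.845, and 0.814 against 0.852: 1.3, 2.0 and 3.8 points lower.

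A further run under other assumptions gave 4 to 7% and 2 to 5 points.

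**6. Responders, if imputed scores were used.** Averaged over failures with the arm's own baseline distribution, 6.0 to 10.5% are imputed as responders in one set of assumptions and 7.1 to 13.4% in another. Patients per arm: 85 × 0.30 × (1/3 to 2/3) = 8.5 to 17; times 6 to 13% gives 0.5 to 2.2. Centred on own baseline with SD 0.7, a patient at 6.1 would need a chance fall of 1.83 (z = 2.61, 0.4%); at 4.0, a fall of 1.2 (z = 1.71, 4%).

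**The case against.** The strongest reply is that the marginal draw is inferred from silence. The text speaks only of a similar distribution, and filling intermittent gaps first leaves a monotone pattern, which is usual preparation for sequential regression on earlier weeks. For dropouts for other reasons this stands: that sentence can be read as ordinary within-arm missing-at-random imputation. A reader might infer that it hands the completers' improvement to non-improvers, but those who leave for lack of response fall under the first rule, and no bias in the second is demonstrated. For the first rule the reply is weaker. The protocol presents these as the specific steps to follow, the reference distribution named is the arm's, and neither document contains any other algorithm.

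A reader might also infer that treatment failures are systematically credited with pain relief. The documents do not support that: low-baseline failures are charged equally large worsening, and baseline is a covariate.

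Nor does any text say that imputed scores feed the responder or time-to-response endpoints. Protocol 7.1 pools only the 120-day results and the MMRM, and the generic Cox code in SAP 13.2 censors patients who leave without responding.

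The protocol never states that each failure should return to their own baseline. The precision argument does not need that aim. The planned supporting analyses are useful, but they do not repair the imputed one.

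**Conclusion.** The point holds for the first rule, as a modest loss of precision and an incomplete specification. Read literally, the arm draw makes the primary ANCOVA's standard error about 2 to 7% larger and costs about 1 to 5 points of power. It shifts the treatment estimate by at most about 0.08 points in the scenarios tried and leaves type I error near 5% when failure rates are equal. The power figure is not universal: it reverses where active failures are more frequent and have high baselines. Chance responders would number roughly 1 to 2 per arm, and only if imputed scores are used for those endpoints. Baseline distribution, dropout mix and week-to-week SD are all assumed. Whether the rule would run at all is unresolved while SAP 7.2 says the opposite.

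**What to change.** 1. Reconcile Protocol 7.1 with SAP 7.2 and put one missing-data rule in the SAP, including whether imputed scores are used for the responder and time-to-response endpoints.
2. If imputation is kept, for adverse-event or lack-of-response dropouts impute each missing weekly score as the patient's own 7-day baseline mean plus a draw from the within-patient week-to-week residual distribution. The reason category also appears to lack a conjunction between adverse event and lack of response; complete it.
3. For other dropouts, state that the within-arm PROC MI model is monotone regression conditional on own baseline and all earlier weekly means. This clarifies wording that may already mean it.

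The cost is protocol and SAP wording plus a few lines of PROC MI code. No new data are needed.

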7.2 Evaluating the Effect of Clinical Sites

This is a multi-center clinical study, with standardization of patient enrollment, data entry, and adverse event reporting. All clinical sites will follow the requirements of the use of the device, data collection procedures, diaries and case report forms. To present the data from this clinical study in a summarized form, a comparison of the primary endpoint results across clinical sites will be performed to determine if the response among sites is consistent. Small sites (i.e., sites that have less than 6 patients) will be identified and the following method will be used for combining the data. Data from all small sites (<6 patients) will be combined to form a single site in order to obviate non-estimable estimates in the evaluation of site and site interaction effects. Once combined, the pooled site will remain in the model for all analyses where a site effect is to be determined. If the pooled smaller sites represent a single site that has more than twice as many patients as the largest single site, however less than 3 times as many patients, the small sites will be ranked by size and divided into 2 pooled assignments using an alternating sequence (ABABAB). If the pooled smaller sites represent a site that has more than three times as many patients as the largest single site, however less than four times as many patients, the small sites will be ranked by size and divided into 3 pooled assignments using an alternating sequence (ABCABCABC).

The statistical test to evaluate poolability for binomial and multinomial variables will be a test of homogeneity comparing the proportions of patients with a positive outcome for the endpoints across clinical sites; a p-value less than 0.1 will be considered evidence of non-poolability. Even with the absence of statistical significance, sites with substantial differences in clinical outcomes will be thoroughly investigated.

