3.1.1. Efficacy Assessments and Endpoints

There will be 11 total endpoints from Part A of the protocol (Part B analysis is in a separate SAP); the interest will be in the change from baseline and the differences between active Provant therapy vs. sham.

Primary Endpoint: Absolute change from baseline in pain intensity as measured by the 11-point, numerical pain rating scale (NPRS) (0-10; where 0=no pain, to 10=worst possible pain) through 4 months.

Secondary Endpoint 1: Percentage of patients who have either a 2 point or 30% reduction in NPRS at 4 Months.

Secondary Endpoint 2: Time to 30% or 2-point reduction in NPRS, whichever comes first at 4 Months.

Secondary Endpoint 3: Change in neuropathy related quality of life (NeuroQoL) between baseline and end of treatment at 4 Months.

Secondary Endpoint 4: Changes in Skin Perfusion Pressure (SPP) from baseline to end of treatment at 4 Months.

Secondary Endpoint 5: Changes in Nerve Conduction Studies (NCS) of Velocity and/or Amplitude between baseline and end of treatment at 4 Months.

Secondary Endpoint 6: Changes in Quantitative Sensory Testing (QST) between baseline and end of treatment at 4 Months.

Secondary Endpoint 7: Change in Patient Global Impression (PGI) at 4 Months.

Exploratory Endpoint 1: Change in Work Productivity and Impairment Questionnaire (WPAIQ) **Exploratory Endpoint 2:** Changes in intraepidermal nerve fiber density (IENFD) at the distal thigh.

Exploratory Endpoint 3: Changes in IENFD at the distal leg.

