11. EFFICACY EVALUATIONS

The primary endpoint for the study is the change from baseline in the NPRS score at 4 months. The primary hypothesis to be tested is presented below:

Ho: μ (Change in NPRS score at 4 months / PEMF group) = μ (Change in NPRS score at 4 months / sham group)

Ha: μ (Change in NPRS score at 4 months / PEMF group) $\neq \mu$ (Change in NPRS score at 4 months / sham group)

To compare the absolute change in pain from baseline to 4-months, the intra-patient change will be calculated and serve as the dependent variable in the analysis. The baseline pain score will be introduced in the model as a covariate. Clinical site will be added to the model to assess poolability of the data across sites. Interaction between clinical site and treatment will be evaluated using a type 1 error rate of 10%. A Mixed Models with Repeated Measures (MMRM) analysis comparing results across all time-points will also be performed, adjusted for the baseline value, week, treatment by week interaction and the effect of the patient.

The primary efficacy endpoint will be summarized and reported using the Level 3 table design. Results will be presented in Table 14.4.1.1 entitled Summary of the Pain Intensity by Randomized Treatment Assignment and Time (ITT Population)

Listing 16.2.8.1 entitled *Pain Intensity by Randomized Treatment Assignment and Time* will contain all of the recorded information; this listing will be sorted by subject number and relative study day.

A list of additional summary tables is presented in the table below.

Table	Description
14.4.1.1.1	Kaplan-Meier Estimates for the First Week where a Mean Reduction of 2 Points or a 30% Reduction from Baseline in the NPRS is Observed
14.4.1.1.2	Summary of the Pain Intensity Categorized by Success (>=30% reduction from baseline) by Randomized Treatment Assignment and Time
14.4.1.1.3	Summary of the Pain Intensity Categorized by Success (>=2 point reduction from baseline) by Randomized Treatment Assignment and Time
14.4.1.1.4	Summary of the Pain Intensity Categorized by Success (>=2 point reduction or 30% reduction from baseline) by Randomized Treatment Assignment and Time

Table	Description
14.4.1.2	Summary of the NeuroQoL Results by Question, Randomized Treatment Assignment and Time
14.4.1.2.1	Summary of the Efficacy Endpoints by Randomized Treatment Assignment and Time - NeuroQol (Weighted) Domain 1: Pain

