(exp(estimate-SE*1.96), exp(estimate+SE*1.96)).

3) SAS (version 9.2) code for the ANOVA models for analyzing efficacy parameters

PROC GLM DATA=inputdataset;

CLASS TREATMENT CENTER;

MODEL variable = TREATMENT CENTER BASELINE;

** differences with CONTROL;

ESTIMATE "ACTIVE-CONTROL" TREATMENT -1 1 / cl alpha=.05;

The values are obtained from ODS data sets as shown in the next table:

Statistical Quantity	ODS Data Set	Record Identifier in ODS	Variable
Estimates by treatment	LSMEANS	TREAT=1 etc.	LSMEAN
Estimates of treatment difference	ESTIMATES	LABEL='TREATMENT- CONTROL'	ESTIMATE
CI on treatment difference	ESTIMATES	LABEL='TREATMENT- CONTROL'	LOWER, UPPER
P-value for treatment difference	ESTIMATES	LABEL='TREATMENT - CONTROL'	PROBT

For subgroup analyses including a discrete covariate such as gender, include the term as follows:

PROC GLM DATA=inputdataset;

CLASS TREATMENT CENTER GENDER;

MODEL variable = TREATMENT CENTER GENDER BASELINE;

PROC GLM DATA=inputdataset;

CLASS TREATMENT CENTER GENDER;

MODEL variable = TREATMENT CENTER GENDER TREATMENT*GENDER BASELINE;

4) SAS (version 9.2) code for the confidence intervals on means

PROC UNIVARIATE DATA=inputdataset CIBASIC; VAR value;

where VALUE is the analysis variable. Confidence intervals are obtained from the BASICINTERVALS ODS data set. The confidence interval is from the LOWERCL and UPPERCL variables on the record where UPCASE(VARNAME) EQ 'MEAN'.

5) SAS code for analyses using PROC FREQ

PROC FREQ DATA = thedataset; TABLES response*group / CHISQ;

The p-value comparing GROUPs is taken from the PROB variable in the ODS EXACT dataset. The record for the Fisher's exact test is the record for which UPCASE(STATISTIC) EQ "FISHER".

6) SAS code for CMH analyses

PROC FREQ DATA = the dataset; TABLES strata*treatment*response / CMH;

The following table shows the sources of the values obtained from the Output Delivery System data sets.

Statistical Quantity	ODS Data Set	Record Identifier in ODS	Variable
P-value for treatment	СМН	UPCASE(ALTHYPOTHESIS) =ROW MEAN SCORES DIFFER	PROBF

where RESPONSE is the variable being analyzed, and strata is the variable being controlled for (e.g., CENTER).

7) SAS code for Cochran-Mantel-Haenszel (CMH) analyses with ordered response (Van Elteren test)

PROC FREQ DATA = thedataset;

TABLES strata* treatment*response / CMH SCORES=MODRIDIT;

8) SAS code for 2-sample Wilcoxon test

PROC NPAR1WAY WILCOXON DATA=inputdataset;

CLASS TREATMENT;

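### For categorical endpoints, Protocol 7.2 judges poolability by differences in response level between sites, not by differences in the device effect between sites

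*Protocol*

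**What the plan says.** Protocol 7.2 sets the poolability test for binomial and multinomial variables as "a test of homogeneity comparing the proportions of patients with a positive outcome for the endpoints across clinical sites", and adds that "a p-value less than 0.1 will be considered evidence of non-poolability". The sentence mentions no arm, no active-sham difference and no interaction. The section then says: "Even with the absence of statistical significance, sites with substantial differences in clinical outcomes will be thoroughly investigated". That safeguard also concerns outcomes by site, not treatment effects.

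The main endpoint concerned is Secondary Endpoint 1, listed first among the secondaries: "Percentage of patients who have either a 2 point or 30% reduction in NPRS at 4 Months".

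The continuous primary endpoint is treated differently. SAP 11 says "Clinical site will be added to the model to assess poolability of the data across sites", and Protocol 7.1 and SAP 11 both go on to the interaction. In the protocol's words, "Interaction between clinical site and treatment will be evaluated using a type 1 error rate of 10" percent.

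No other section supplies a treatment-by-site test for the categorical endpoints. Protocol 7.2 refers to site interaction only when justifying the small-site rule ("Small sites (i.e., sites that have less than 6 patients) will be identified"). SAP 7.1 has its own small-site rule but no categorical poolability test. SAP 13.2 offers generic stratified code ("TABLES strata*treatment*response / CMH"), takes only the treatment p-value from it, and asks for no test of whether the effect is the same across strata.

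**The concern.** Pooling across sites is in doubt if the active-sham contrast differs by site. It is not in doubt merely because some sites see more responders than others in both arms. Protocol 3.6 stratifies the 1:1 randomisation by site, so the arms are about balanced within each site, and a difference in overall level cancels from the within-site comparison.

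A test of combined response rates can therefore go wrong in two ways. It can label sound data non-poolable because sites differ in case mix or in how patients score pain. It can also return a non-significant result when the device effect varies between sites, and that result could then be cited as reassurance on a question it did not address. The plan does not say how the analysis should respond to a flag, so a false one would invite an unplanned response.

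**Working it through.** **Inputs from the documents.** 170 patients, 85 per arm (Protocol 7.4); up to 20 sites (synopsis), so as few as 170/20 = 8.5 patients per site on average; 1:1 randomisation stratified by site (3.6); threshold p < 0.1 (7.2); planning change 1.79, SD 1.83, difference 1.07 (7.4).

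**Plan's own figure.** The point does not rest on the sample size, but the planning inputs are used below, so I checked them. n per arm = 2(1.960 + 1.282)² × 1.83² / 1.07² ≈ 61.5, which rounds up to the stated 62.

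**Check by hand (no simulation).** Take 8 sites with 10 patients per arm. With overall response 80/160 = 0.5, each site's expected total is 10 of 20, with variance 20 × 0.5 × 0.5 = 5.

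1. *Effect reversed.* Active/sham responders are 7/3 in four sites and 3/7 in the other four. Every site has 10/20, so chi-square = 0 and p = 1.00. Breslow-Day for a common odds ratio: the Mantel-Haenszel odds ratio is 1, the expected active count is 5 and its variance is 1/(4/5) = 1.25. The statistic is 8 × (2²/1.25) = 25.6 on 7 df, p = 0.0006.
2. *Effect constant, levels different.* Responders are 4/2 in four sites and 8/6 in the other four. The odds ratio is (4×8)/(6×2) = (8×4)/(2×6) = 2.67 everywhere, and the risk difference is 20 points everywhere. Site totals are 6/20 and 14/20, so the protocol's chi-square = 8 × (4²/5) = 25.6 on 7 df, p = 0.0006. Breslow-Day p = 1.00.

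In these two examples the planned test gives the wrong answer in both directions.

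**Simulation with rates derived from the planning figures.** The documents give no responder rates. At an assumed baseline of about 6, a 30% fall is 1.8 points. Under normality, active response is P(Z > (1.8 − 1.79)/1.83) ≈ 50%. The sham mean is 0.4 × 1.79 = 0.716, so sham response is P(Z > (1.8 − 0.716)/1.83) ≈ 28%. With 8 to 14 sites and about 160 to 168 patients:

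- Same odds ratio everywhere, site levels varying with a logit SD of 0.5 (assumed): flagged in 43 to 52% of trials, and in 46 to 50% in a repeat. At SD 0.8: 82 to 84%.
- Effect fully reversed in half the sites, no site main effect: flagged in 7 to 9%, and in 7 to 8% in a repeat.

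**Simulation with simpler assumed rates.** 160 patients; 20, 10 or 8 equal sites; 4,000 runs each; both tests at p < 0.1.

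| Scenario | Protocol's test | Breslow-Day |
|---|---|---|
| No site differences (sham 30%, active 50%) | 6.5–7.7% | 12–17% |
| Constant +20 points, sham 20% or 40% by site | 31–53% | 11–17% |
| Constant +20 points, sham 15% or 55% by site | 95–99% | 11–14% |
| Balanced reversal (active/sham 60/30 and 30/60) | 4–6% | 83–90% |
| Lopsided: sham 40%, active 60% or 20% by site | 31–52% | 53–61% |
| Lopsided: sham 40%, active 70% or 10% by site | 64–88% | 86–94% |

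The protocol's test runs below 10% under balanced reversal because mixing two arms with different rates gives less variance than a binomial at the mean rate. With 60% and 30% the actual variance per patient is (0.24 + 0.21)/2 = 0.225, against the assumed 0.45 × 0.55 = 0.2475.

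**The case against.** A reader might infer that the planned test cannot see a varying device effect at all. The documents do not support that. The low flag rate arises when the reversal leaves each site's combined rate unchanged. With lopsided differences the combined rates move, and the test picks up part of it: 31 to 88% in the table. With sham at 28% everywhere and active at 50% or 6% by site, it flags 57 to 70%, against 66 to 78% for an interaction test. The gap is modest there, and part of it reflects the interaction test exceeding its nominal level.

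A reader might also infer that the trial's efficacy conclusion is exposed. Three facts limit this.

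- The primary endpoint has its own interaction test at 10%. Secondary Endpoint 1 dichotomises the same NPRS change, so a reversing effect could surface there.
- Protocol 7.2 excludes no site and changes no model when a flag is raised. Its only stated follow-up is investigation of sites.
- A full reversal in half the sites averages to no effect. In simulation the overall responder comparison significantly favoured active in only about 2% of trials.

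The SAP, to which the protocol delegates detail, does not carry the sentence. Comparing site response rates is also a legitimate descriptive check, since the section's stated aim includes consistency of response among sites. The false-flag rates depend on assumed site variation for which the documents give no figure.

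All of this narrows the point. None of it makes a site main effect evidence against pooling the treatment comparison, and the SAP's silence leaves the protocol's sentence as the only categorical criterion.

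**Conclusion.** The point holds for categorical endpoints, chiefly the responder rate. The criterion in Protocol 7.2 tests whether sites differ in response level. Such differences are harmless to a comparison randomised within site, yet they can make the test call valid data non-poolable: about 45 to 50% of trials at an assumed site logit SD of 0.5, and 82 to 84% at 0.8. It has no useful power when the effect differs between sites while combined rates stay about equal (about 7 to 8% flagged in a balanced reversal), and it detects lopsided differences only indirectly.

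The percentages rest on assumed responder rates, site layouts and site variation. The direction of the error does not, as the hand check shows. The primary analysis is not affected, and no analysis changes automatically on a flag. The point should be corrected, but it does not threaten the trial's main conclusion.

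**What to change.** In Protocol 7.2, replace the criterion for binomial and multinomial endpoints by a treatment-by-site interaction test at the same 10% level on the pooled-site factor:

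- binary endpoints: a logistic treatment-by-site term, or an exact test of homogeneity of odds ratios where sites are small;
- multinomial endpoints: the matching interaction in an ordinal model if the categories are ordered, otherwise in a nominal one.

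Add the same sentence to the SAP, where it would be new text. State which small-site rule defines the factor: Protocol 7.2 pools sites with fewer than 6 patients, whereas SAP 7.1 pools those with fewer than 2 in any arm. Keep site response rates as a descriptive display, and say that they do not count as evidence of non-poolability.

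The cost is a sentence in each document, with no new data. The drawbacks are low power at these site sizes and, for large-sample versions, a rejection rate above nominal: Breslow-Day gave 12 to 17% at a nominal 10% with no site differences. That is the reason for offering an exact test where sites are small.
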